4. PROTOCOL COORDINATION, FUNDING, MODE

Regulatory Sponsor:

DF/HCC Investigator [name]

Funding/Support (check all that apply):

Primary Disease Group: GYN Oncology

Industry: Merck

Federal Organization:

Grant #:

Internal Funding:

Non-Federal:

Other:

Protocol Involves (check all that apply as listed in the protocol document, even if not part of the research but is mandated by the protocol document):

Chemotherapy

Hormone Therapy

Medical Record Review

Immunotherapy

Vaccine

Questionnaires/Surveys/Interviews

Surgery

Engineered Cell Therapy (ECT)

Radiological Exams

Bone Marrow/Stem Cell Transplant

Data Repository

Required Biopsy Study

Cell Based Therapy

Exercise/Physical Therapy

Human Embryonic Stem Cell

Gene Transfer (use of recombinant DNA or synthetic nucleic acid molecules)

Genetic Studies

Quality of Life

Radiation Therapy

Human Material Banking

Other:

Human Material Collection

5. SUBJECT POPULATION (also applies to medical record review and specimen collection studies)

Total Study-Wide Enrollment Goal: 26

Greater than 25% of the overall study accrual will be at DF/HCC: Yes No

Total DF/HCC Estimated Enrollment Goal: 26

Adult Age Range: 18+

Pediatric Age Range: N/A

Will all subjects be recruited from pediatric clinics? Yes No

If enrolling both adults and pediatric subjects, anticipated percent of pediatric subjects: N/A

Retrospective Medical Record Reviews only (Please provide date range): from _____ to _____

6. DF/HCC PARTICIPANTS UNDER DFCI IRB (check all that apply)

Beth Israel Deaconess Medical Center (BIDMC)

Beth Israel Deaconess Medical Center – Needham (BIDMC-Needham)

Boston Children's Hospital (BCH)

Dana-Farber/New Hampshire Oncology-Hematology (DFCI @ NHOH)

Brigham and Women's Hospital (BWH)

Dana-Farber at Steward St. Elizabeth's Medical Center (DFCI @ SEMC)

Dana-Farber Cancer Institute (DFCI)

Dana-Farber at Milford Regional Cancer Center (DFCI @ MRCC)

Massachusetts General Hospital (MGH)

Mass General/North Shore Cancer Center (MGH @ NSCC)

Massachusetts General Hospital – Emerson Hospital – Bethke (MGH @ EH)

DF/BWCC in Clinical Affiliation with South Shore Hospital (DFCI @ SSH)

7. NON-DF/HCC PARTICIPANTS UNDER DFCI IRB (check all that apply)

Cape Cod Healthcare (CCH)

Faulkner Hospital (FH)

Lowell General Hospital (LGH)

New England Cancer Specialists (NECS)

New Hampshire Oncology-Hematology-P.A. (NHOH)

Broad Institute

Newton-Wellesley Hospital (NWH)

Protocol Front Sheet

1. OBJECTIVES

1.1 Study Design

This is a phase II study with a safety lead in of the combination of the recommended phase II doses of pegylated liposomal doxorubicin (PLD) and pembrolizumab for the treatment of platinum resistant recurrent ovarian, fallopian tube or peritoneal cancer.

1.2 Primary Objectives

1.2.1 To assess the clinical benefit (complete response + partial response or stable disease > 24 weeks) of the combination of PLD and pembrolizumab in patients with platinum resistant recurrent ovarian cancer. Initially, a six patient safety lead in will be performed of these 2 drugs combined together when used to treat patients with recurrent ovarian, peritoneal or fallopian tube cancer. If no more than 1 patient of the first 6 patients has evidence of dose limiting toxicities, an additional 20 patients will be added to complete the phase II study.

1.3 Secondary Objectives

1.3.1 To gain an estimate of toxicities for these agents when combined to treat platinum resistant recurrent ovarian, fallopian tube or peritoneal cancer

1.3.2 To gain an estimate of preliminary response rate for these agents when combined for the treatment of platinum resistant ovarian cancer, progression free survival (PFS), overall survival (OS), time to progression (TTP), and duration of response.

1.3.3 To perform exploratory translational studies on formalin fixed paraffin embedded tumor that include nanostring as well as PDL1 and exploratory immune markers.

2. BACKGROUND

2.1 Study Disease: Ovarian Cancer

Ovarian cancer is a lethal cancer that affects women globally, is diagnosed at an advanced stage in most patients and has no effective screening tests for early detection (1-3). The worldwide incidence of this cancer is 225,500 diagnoses per year; in the United States in 2015, approximately 21,980 women will be diagnosed with ovarian cancer (1, 2). Global mortality of this cancer remains high with 140,200 deaths per year, and minimal improvement in mortality has been observed for women diagnosed with advanced ovarian cancer over the past decade (1, 2).

Treatment strategies that have led to an overall survival (OS) improvement for newly diagnosed patients have included the addition of paclitaxel to platinum, the use of intraperitoneal cisplatin in patients with optimally cytoreduced cancer (<1 cm of residual cancer after upfront

cytoreductive surgery), and incorporation of weekly paclitaxel versus every 3 week paclitaxel as part of upfront treatment for ovarian cancer (4-6). Neoadjuvant chemotherapy has emerged as a treatment alternative especially in patients who are unable to undergo upfront cytoreductive surgery because of the extent of cancer or those patients who are too ill or frail to undergo upfront cytoreductive surgery (7, 8). Anti-angiogenics, specifically bevacizumab, were the first biologic to be tested in ovarian cancer but to date addition of bevacizumab in randomized trials has demonstrated progression free survival (PFS) benefit, but no OS benefit (9-11).

Unfortunately, most patients will recur after being diagnosed with advanced ovarian cancer; for patients with platinum-sensitive recurrence (defined as cancer recurring ≥ 6 months after the last platinum), additional platinum-based therapy is given. For patients with recurrent platinum resistant cancer (defined as cancer recurring < 6 months after last platinum), single agent chemotherapy is administered. New agents and rationale combinations of biologics and chemotherapy are needed to improve outcomes in women with recurrent ovarian cancer, such as chemotherapy combined with immunotherapy agents. The first 2 agents since the last approval in 2006 (carboplatin and gemcitabine for platinum sensitive recurrence) were approved by the Food and Drug Administration (FDA) in 2014: bevacizumab in combination with chemotherapy in patients with platinum resistant ovarian cancer and the oral PARP inhibitor olaparib for women with a *gBRCA* mutation, recurrent ovarian cancer and who have received at least 3 lines of prior chemotherapy.

Many chemotherapy options exist for women with recurrent ovarian cancer but none of them are curative, and most agents used in the platinum resistance recurrent setting have response rates that are 10% or less. Pegylated liposomal doxorubicin (PLD) is a standard of care treatment for recurrent ovarian cancer (12-14).

2.2 Pegylated Liposomal Doxorubicin (PLD)

PLD is approved in the U.S., Canada, and Europe for use in ovarian cancer following progression of cancer after platinum-based chemotherapy and represents a standard of care treatment for women with relapsed ovarian cancer (15).

PLD has demonstrated anti-cancer activity in both phase II and III studies; phase III studies have compared PLD to topotecan as well as other agents. Response rates for platinum resistant recurrent ovarian cancer are approximately 10%. Progression-free survival (PFS) for PLD in patients with recurrent ovarian cancer is approximately 3-4 months (12-14). Known toxicities of PLD include: hand-foot syndrome, mucositis, cardiotoxicity, myelosuppression, liver impairment, and infusion-related reactions. See the PLD Package Insert for other reported toxicities and additional details of clinical studies as well as toxicity management.

2.3 Pembrolizumab

Refer to the Investigator's Brochure (IB)/approved labeling for detailed background information on MK-3475.

The importance of intact immune surveillance in controlling outgrowth of neoplastic

transformation has been known for decades. Accumulating evidence shows a correlation between tumor-infiltrating lymphocytes (TILs) in cancer tissue and favorable prognosis in various malignancies. In particular, the presence of CD8+ T-cells and the ratio of CD8+ effector T-cells / FoxP3+ regulatory T-cells seems to correlate with improved prognosis and long-term survival in many solid tumors.

The PD-1 receptor-ligand interaction is a major pathway hijacked by tumors to suppress immune control. The normal function of PD-1, expressed on the cell surface of activated T-cells under healthy conditions, is to down-modulate unwanted or excessive immune responses, including autoimmune reactions. PD-1 (encoded by the gene *Pdcd1*) is an Ig superfamily member related to CD28 and CTLA-4 which has been shown to negatively regulate antigen receptor signaling upon engagement of its ligands (PD-L1 and/or PD-L2). The structure of murine PD-1 has been resolved. PD-1 and family members are type I transmembrane glycoproteins containing an Ig Variable-type (V-type) domain responsible for ligand binding and a cytoplasmic tail which is responsible for the binding of signaling molecules. The cytoplasmic tail of PD-1 contains 2 tyrosine-based signaling motifs, an immunoreceptor tyrosine-based inhibition motif (ITIM) and an immunoreceptor tyrosine-based switch motif (ITSM). Following T-cell stimulation, PD-1 recruits the tyrosine phosphatases SHP-1 and SHP-2 to the ITSM motif within its cytoplasmic tail, leading to the dephosphorylation of effector molecules such as CD3 ζ , PKC θ and ZAP70 which are involved in the CD3 T-cell signaling cascade. The mechanism by which PD-1 down modulates T-cell responses is similar to, but distinct from that of CTLA-4 as both molecules regulate an overlapping set of signaling proteins. PD-1 was shown to be expressed on activated lymphocytes including peripheral CD4+ and CD8+ T-cells, B-cells, Tregs and Natural Killer cells. Expression has also been shown during thymic development on CD4-CD8- (double negative) T-cells as well as subsets of macrophages and dendritic cells. The ligands for PD-1 (PD-L1 and PD-L2) are constitutively expressed or can be induced in a variety of cell types, including non-hematopoietic tissues as well as in various tumors. Both ligands are type I transmembrane receptors containing both IgV- and IgC-like domains in the extracellular region and contain short cytoplasmic regions with no known signaling motifs. Binding of either PD-1 ligand to PD-1 inhibits T-cell activation triggered through the T-cell receptor. PD-L1 is expressed at low levels on various non-hematopoietic tissues, most notably on vascular endothelium, whereas PD-L2 protein is only detectably expressed on antigen-presenting cells found in lymphoid tissue or chronic inflammatory environments. PD-L2 is thought to control immune T-cell activation in lymphoid organs, whereas PD-L1 serves to dampen unwarranted T-cell function in peripheral tissues. Although healthy organs express little (if any) PD-L1, a variety of cancers were demonstrated to express abundant levels of this T-cell inhibitor. PD-1 has been suggested to regulate tumor-specific T-cell expansion in participants with melanoma (MEL). This suggests that the PD-1/PD-L1 pathway plays a critical role in tumor immune evasion and should be considered as an attractive target for therapeutic intervention.

Pembrolizumab is a potent and highly selective humanized monoclonal antibody (mAb) of the IgG4/kappa isotype designed to directly block the interaction between PD-1 and its ligands, PD-L1 and PD-L2. KeytrudaTM (pembrolizumab) has recently been approved in the United States for the treatment of patients with unresectable or metastatic melanoma and disease progression following ipilimumab and, if BRAF V600 mutation positive, a BRAF inhibitor.

2.4 Rationale

2.4.1 Rationale for testing PLD and pembrolizimab in recurrent ovarian cancer

The rationale to combine the anti-PD1 monoclonal antibody pembrolizumab with chemotherapy to treat ovarian cancer includes the following:

- 1) PDL1 is overexpressed in ovarian cancer and PD1 is overexpressed in TILs. The presence of TILs in advanced stage ovarian carcinomas predicts for a better overall outcome with improved PFS and OS compared to those cancers which lack TILs (1,2). Increased frequency of Treg cells in patients with ovarian cancer can predict a poorer survival.
- 2) Anti-cancer synergy has been demonstrated with anti-PD1 antibodies and chemotherapy (16-18). Several clinical trials are open using both chemotherapy and immunotherapy agents.
- 3) Reduction in tumor burden through chemotherapy can potentiate an immune response, thus the rationale exists to combine a chemotherapy agent such as PLD with a PD1 inhibitor (16-18).

2.4.2 Rationale for flat dose of pembrolizumab

An open-label Phase I trial (Protocol 001) is being conducted to evaluate the safety and clinical activity of single agent MK-3475. The dose escalation portion of this trial evaluated three dose levels, 1 mg/kg, 3 mg/kg, and 10 mg/kg, administered every 2 weeks (Q2W) in participants with advanced solid tumors. All three dose levels were well tolerated and no dose-limiting toxicities were observed. This first in human study of MK-3475 showed evidence of target engagement and objective evidence of tumor size reduction at all dose levels (1 mg/kg, 3 mg/kg and 10 mg/kg Q2W). No MTD has been identified to date. 10.0 mg/kg Q2W, the highest dose tested in PN001, will be the dose and schedule utilized in Cohorts A, B, C and D of this protocol to test for initial tumor activity. Recent data from other clinical studies within the MK-3475 program has shown that a lower dose of MK-3475 and a less frequent schedule may be sufficient for target engagement and clinical activity.

PK data analysis of MK-3475 administered Q2W and Q3W showed slow systemic clearance, limited volume of distribution, and a long half-life (refer to IB). Pharmacodynamic data (IL-2 release assay) suggested that peripheral target engagement is durable (>21 days). This early PK and pharmacodynamic data provides scientific rationale for testing a Q2W and Q3W dosing schedule.

A population pharmacokinetic analysis has been performed using serum concentration time data from 476 patients. Within the resulting population PK model, clearance and volume parameters of MK-3475 were found to be dependent on body weight. The relationship between clearance and body weight, with an allometric exponent of 0.59, is within the range observed for other antibodies and would support both body weight normalized dosing or a fixed dose across all body weights. MK-3475 has been found to have a wide therapeutic range based on the melanoma indication. The differences in exposure for a 200 mg fixed dose regimen relative to a 2 mg/kg Q3W body weight based regimen are anticipated to remain well within the established

exposure margins of 0.5 – 5.0 for MK-3475 in the melanoma indication. The exposure margins are based on the notion of similar efficacy and safety in melanoma at 10 mg/kg Q3W vs. the proposed dose regimen of 2 mg/kg Q3W (i.e. 5-fold higher dose and exposure). The population PK evaluation revealed that there was no significant impact of tumor burden on exposure. In addition, exposure was similar between the NSCLC and melanoma indications. Therefore, there are no anticipated changes in exposure between different indication settings.

The rationale for further exploration of 2 mg/kg and comparable doses of pembrolizumab in solid tumors is based on: 1) similar efficacy and safety of pembrolizumab when dosed at either 2 mg/kg or 10 mg/kg Q3W in melanoma patients, 2) the flat exposure-response relationships of pembrolizumab for both efficacy and safety in the dose ranges of 2 mg/kg Q3W to 10 mg/kg Q3W, 3) the lack of effect of tumor burden or indication on distribution behavior of pembrolizumab (as assessed by the population PK model) and 4) the assumption that the dynamics of pembrolizumab target engagement will not vary meaningfully with tumor type.

The choice of the 200 mg Q3W as an appropriate dose for the switch to fixed dosing is based on simulations performed using the population PK model of pembrolizumab showing that the fixed dose of 200 mg every 3 weeks will provide exposures that 1) are optimally consistent with those obtained with the 2 mg/kg dose every 3 weeks, 2) will maintain individual patient exposures in the exposure range established in melanoma as associated with maximal efficacy response and 3) will maintain individual patients exposure in the exposure range established in melanoma that are well tolerated and safe.

A fixed dose regimen simplifies the dosing regimen to be more convenient for physicians and to reduce potential for dosing errors. A fixed dosing scheme will also reduce complexity in the logistical chain at treatment facilities and reduce wastage.

2.5 Correlative Studies Background

FFPE will be collected for exploratory immune markers as tested by immunohistochemical (IHC) staining of specific markers and PDL1 expression to be done at Merck.

1) Formalin fixed-paraffin embedded (FFPE) tumor slices will be prepared and H&E stained for assessment of TIL in tumor samples. To identify different immune cell populations (effector/memory/ CD8 cells, T regulatory cells, dendritic cells, tumor associated macrophages, NK cells, TEM) IHC staining will be performed on FFPE tumor slices using the following antibodies: CD3, CD4, CD8, CD25, FoxP3, Indoleamine 2,3 deoxygenase-1 (IDO), CD11c, CD83, CD86, CD56, CD14, and CD16. Also included will be recently developed IHC staining on FFPE samples for PD-L1, PD-L2, TIM-3 and LAG-3 through the center for Immun-oncology Pathology Core at the Dana-Farber Cancer Institute ([name]., Ph.D. Core Director).

2) PDL1 IHC staining at Merck: Merck has asked that tumor samples also be sent to their facility for PDL1 staining using their technique and staining. QualTek has developed and validated a PD-L1 IHC assay using Merck's proprietary 22C3 antibody. This assay has served as the prototype companion diagnostic assay and has been used by QualTek to test thousands of clinical samples, including those for prospective enrollment in other clinical trials. The PD-L1 IHC assay has been validated and tested in over 20 different tumor indications in various clinical

studies and on thousands of archived FFPE samples.

3) Nanostring analysis will be performed at Merck. Merck will perform gene profiling analysis using the nanostring platform to identify new biomarkers and gain insight to molecular basis of anti-PD-1 resistance with samples from this study. For each patient enrolled in the study, 4 unstained slides (4-5 micron sections) per sample of FFPE tumor will be sent to Merck. Samples will be analyzed for gene expression using nanostring which is an 800 gene immune-response focused panel and results will be shared with the overall PI, [name].

3. PARTICIPANT SELECTION

3.1 Participant Inclusion Criteria

In order to be eligible for participation in this trial, the participant must meet the following eligibility criteria:

- 3.1.1 Be willing and able to provide written informed consent/assent for the trial.
- 3.1.2 Be \geq 18 years of age on day of signing informed consent.
- 3.1.3 Have measurable disease based on RECIST 1.1 criteria.
- 3.1.4 Have a histologically confirmed diagnosis of epithelial ovarian cancer, fallopian tube or peritoneal cancer. All histologies of epithelial ovarian cancer are eligible except for carcinosarcomas.
- 3.1.5 Patients must have had one prior platinum-based chemotherapeutic regimen for management of primary disease containing carboplatin, cisplatin, or another organoplatinum compound. This initial treatment may have included intraperitoneal therapy, consolidation, biologic/targeted (non-cytotoxic) agents (e.g., bevacizumab) or extended therapy administered after surgical or non-surgical assessment.
- 3.1.6 Patients must have platinum resistant cancer with a platinum free interval of < 6 months. Progression after last platinum is based on investigator assessment.
- 3.1.7 Patients are allowed to receive, but are not required to receive, up to two additional cytotoxic regimens for management of recurrent or persistent disease, with no more than 1 prior non-platinum cytotoxic chemotherapeutic regimen.

Patients are allowed to receive, but are not required to receive, biologic/targeted (non-cytotoxic) therapy as part of prior treatment. For the purposes of this study, Poly (ADP-ribose) polymerase (PARP) inhibitors will be considered “cytotoxic.” Patients are allowed to receive, but are not required to receive, PARP inhibitors for management of primary or recurrent/persistent disease (either alone or in combination with cytotoxic chemotherapy). Single agent hormonal therapies will not be counted as a line of treatment.

- 3.1.8 Have confirmation of available tissue from an archived specimen of ovarian cancer. If there is no archival tissue available, the participant will be required to undergo a biopsy to obtain a fresh tumor sample.
- 3.1.9 Have a performance status of 0 or 1 on the ECOG Performance Scale (Appendix A).
- 3.1.10 Demonstrate adequate organ function as defined in Table 1, all screening labs must be performed within 14 days of treatment initiation.

Table 1 Adequate Organ Function Laboratory Values

System	Laboratory Value
Hematological	
Absolute neutrophil count (ANC)	$\geq 1,500 / \mu\text{L}$
Platelets	$\geq 100,000 / \mu\text{L}$
Hemoglobin	$\geq 9 \text{ g/dL}$ or $\geq 5.6 \text{ mmol/L}$ without transfusion or EPO dependency (within 7 days of assessment)
Renal	
Serum creatinine OR Measured or calculated ^a creatinine clearance (GFR can also be used in place of creatinine or CrCl)	$\leq 1.5 \times$ upper limit of normal (ULN) OR $\geq 60 \text{ mL/min}$ for participant with creatinine levels $> 1.5 \times$ institutional ULN
Hepatic	
Serum total bilirubin	$\leq 1.5 \times$ ULN OR Direct bilirubin \leq ULN for participants with total bilirubin levels $> 1.5 \times$ ULN
AST (SGOT) and ALT (SGPT)	$\leq 2.5 \times$ ULN OR $\leq 5 \times$ ULN for participants with liver metastases
Albumin	$\geq 2.5 \text{ g/dL}$
Coagulation	
International Normalized Ratio (INR) or Prothrombin Time (PT)	$\leq 1.5 \times$ ULN unless participant is receiving anticoagulant therapy as long as PT or PTT is within therapeutic range of intended use of anticoagulants
Activated Partial Thromboplastin Time (aPTT)	$\leq 1.5 \times$ ULN unless participant is receiving anticoagulant therapy as long as PT or PTT is within therapeutic range of intended use of anticoagulants

^aCreatinine clearance should be calculated per institutional standard.

- 3.1.11 Female participants of childbearing potential must have a negative serum pregnancy within 72 hours prior to receiving the first dose of study medication. If the urine test is positive or cannot be confirmed as negative, a serum pregnancy test will be required.
- 3.1.12 Female participants of childbearing potential must be willing to use 2 methods of birth control or be surgically sterile, or abstain from heterosexual activity for the course of the study through 120 days after the last dose of study medication. Participants of childbearing potential are those who have not been surgically sterilized or have not been free from menses for > 1 year.

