3.2 Participant Exclusion Criteria

The participant must be excluded from participating in the trial if the participant has any of

the following:

- 3.2.1 Is currently participating and receiving study therapy or has participated in a study of an investigational agent and received study therapy or used an investigational device within 4 weeks of the first dose of treatment.
- 3.2.2 Has a diagnosis of immunodeficiency or is receiving systemic steroid therapy or any other form of immunosuppressive therapy within 7 days prior to the first dose of trial treatment.
- 3.2.3 Patients cannot have primary platinum refractory cancer, i.e. documented cancer progression while receiving platinum or within one month of receipt of a platinum based regimen.
- 3.2.4 Has received a prior anthracycline chemotherapy either for ovarian cancer treatment or another previous malignancy.
- 3.2.5 Left ventricular ejection fraction (LVEF) defined by multigated acquisition (MUGA) or echocardiogram which is below the institutional lower limit of normal prior to starting study treatment.
- 3.2.6 Has a known history of active TB (Bacillus Tuberculosis)
- 3.2.7 Known hypersensitivity to pembrolizumab or any of its excipients and/or liposomal doxorubicin.
- 3.2.8 Has had prior chemotherapy, targeted small molecule therapy, or radiation therapy within 2 weeks prior to study Day 1 or who has not recovered (i.e., \leq Grade 1 or at baseline) from adverse events due to a previously administered agent.
 - i. Note: If participant underwent major surgery, they must have recovered adequately from the toxicity and/or complications from the intervention prior to starting therapy.
 - ii. Note: Participants with alopecia are an exception to this criterion.
- 3.2.9 Has a known additional malignancy that is progressing or requires active treatment. In addition, patients cannot have been diagnosed with another malignancy within 3 years of starting treatment. Exceptions include fully resected basal cell carcinoma of the skin or squamous cell carcinoma of the skin, *in situ* cervical cancer, fully resected ductal carcinoma *in situ*, and stage IA, noninvasive grade I endometrial cancer, that has undergone curative therapy.

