10. STUDY CALENDAR

Baseline evaluations are to be conducted within 14 days prior to start of protocol therapy. Baseline labs must be performed within 14 days of treatment initiation. Scans and x-rays must be done ≤ 4 weeks prior to the start of therapy. In the event that the participant's condition is deteriorating, laboratory evaluations should be repeated within 48 hours prior to initiation of the next cycle of therapy.

Assessments must be performed prior to administration of any study agent. Study assessments and agents should be administered within ± 3 days of the protocol-specified date, unless otherwise noted.

	Pre-Study	C1 D1	C1 D8	C1 D15	C1 D22	C2 D1	C2 D15	C3 D1	C3 D8	Cycle 4 and beyond^f	Off Study ^c
PLD ^d		A				A		A		A	
Pembrolizumab ^e		B			B		B		B	B	
Informed consent	X										
Demographics	X										
Medical history	X										
Concurrent meds	X	X-								X ^f	
Physical exam ¹	X	X			X	X	X	X	X	X ^f	X
Vital signs ²	X	X			X	X	X	X	X	X ^f	X
Height and weight ³	X	X			X	X	X	X	X	X ^f	
Performance status ⁴	X	X			X	X	X	X	X	X ^f	X
CA-125	X	X				X		X			X
CBC w/diff, plts	X	X	X	X	X	X	X	X	X	X ^f	X
Serum chemistry ^a	X	X	X	X	X	X	X	X	X	X ^f	X
TSH	X	X				X					X
EKG (as indicated)	X										
Adverse event evaluation		X-								X ^f	X
Tumor measurements	X	Tumor measurements are repeated every 8 weeks ± 1 week weeks. Documentation (radiologic) must be provided for participants removed from study for progressive disease. ^g									X
B-HCG	X ^b										
FFPE blocks ^d	X										
ECHO or MUGA ^e	X									X ^e	

A: PLD 40 mg/m² IV every 28 days ± 3 days window

B: Pembrolizumab 200 mg IV every 21 days ± 3 days window

1: Will include skin examination in addition to physical exam

2: Including blood pressure, temperature, respiratory rate, heart rate

3: Height should be performed at screening and Cycle 1 Day 1 only, weight should be performed at each visit

4: ECOG performance status as per Appendix 1.

5: The schedules for pembrolizumab and doxil can be delayed independently, however, the clock does not stop for each 28 day cycle regarding the cycle/day.

- a: Albumin, alkaline phosphatase, total bilirubin, bicarbonate, BUN, calcium, chloride, creatinine, glucose, LDH, phosphorus, potassium, total protein, SGOT [AST], SGPT [ALT], sodium.
- b: Serum pregnancy test (only for women of childbearing potential).

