13.2 Sample Size, Accrual Rate and Study Duration

Because of the possibility that both objective response and prolongment of progression –free intervals are enhanced when chemotherapy and immune checkpoint blockade inhibitors are combined, the primary endpoint of this study is clinical benefit rate, using an interval of at least 24 weeks of stable disease. Pujade-Lauraine et al reported a 12% objective response rate in control arm to the AURELIA of single-agent chemotherapy for platinum-resistant ovarian cancer; the probability of being progression-free at 6 months was approximately 20%.

Therefore, a true clinical benefit rate of 25% or less would not be of clinical interest, and is the null hypothesis to a binomial test for a single-stage A'Hern design. A true clinical benefit rate of 50% would be considered a clinically meaningful level of response. Sample size was chosen to have high power ($\geq 90\%$) to declare the combination effective at this rate, while controlling the one-sided Type I error at no more than 10% under the null (exact alpha = 0.091)

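### Eligibility requires progression only after the last platinum, so disease already controlled by a later regimen can be counted as clinical benefit

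*Combined protocol and SAP*

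**What the plan says.** **Progression at entry.** Section 3.1.6 reads "Patients must have platinum resistant cancer with a platinum free interval of < 6 months" and adds "Progression after last platinum is based on investigator assessment". Section 3.1.3 asks for measurable disease; it does not ask that the disease be growing.

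**Later treatment.** Section 3.1.7 allows "up to two additional cytotoxic regimens for management of recurrent or persistent disease, with no more than 1 prior non-platinum cytotoxic chemotherapeutic regimen". It also allows "biologic/targeted (non-cytotoxic) therapy as part of prior treatment". PARP inhibitors are classed as cytotoxic, and single-agent hormonal therapy does not count as a line. Nothing in 3.1 or 3.2 requires progression during or after any of these later treatments.

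**Washout and baseline imaging.** Section 3.2.8 excludes a patient who "Has had prior chemotherapy, targeted small molecule therapy, or radiation therapy within 2 weeks prior to study Day 1". The study calendar (section 10) says "Scans and x-rays must be done ≤ 4 weeks prior to the start of therapy". Section 11.1.3 sets the same four-week maximum and asks that baseline evaluations be as near to the start of treatment as possible. Section 5.5.3 prohibits other anticancer therapy during screening and treatment, but no section says when screening begins.

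**Endpoint and test.** Section 13.1 defines clinical benefit as complete response, partial response, or stable disease of 24 weeks or more. Section 13.2 describes this as "using an interval of at least 24 weeks of stable disease". Section 11.1.4 times stable disease from the start of study treatment. Sections 13.2 and 13.4 test a 25% null in a single arm and reject it at 10 or more of 26.

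**The concern.** Stable disease shows a drug effect only if the disease would otherwise have been progressing. Where platinum was the most recent treatment, 3.1.6 secures this. Where a later agent intervened, it does not.

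Take a patient who progressed four months after platinum, received a non-platinum agent, a PARP inhibitor or a biologic, and stopped it for toxicity or completion while stable, with measurable disease remaining. She satisfies the disease-status criteria as written. If she stays stable for 24 weeks from Day 1, she counts as a success of the study combination, although the earlier regimen may have produced that control.

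The trial has no concurrent arm in which such patients would also appear. The comparison is with a fixed 25%, reasoned from a chemotherapy control arm, and no planned analysis separates these patients. For this gap the error runs toward calling the regimen worthy of further study.

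The scan-timing gap is secondary. If the baseline scan precedes the last prior dose, later shrinkage from that dose would be measured against too large a baseline.

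**Working it through.** **1. The plan's own figures.** Inputs from 13.2 and 13.4: n = 26, reject at 10 or more, null 25%, alternative 50%, one-sided type I error at most 10% (stated exact value 0.091), power at least 90%.

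- Type I error: P[Bin(26, 0.25) ≥ 10] = 0.0909, which rounds to the stated 0.091.
- Power: P[Bin(26, 0.50) ≥ 10] = 0.916, which meets the 90% target.

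The design is correctly computed. The margin below the 10% limit is 0.100 − 0.0909 = 0.0091, under one percentage point.

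**2. Effect of patients with prior disease control.** Suppose k of the 26 enter without progression since a later regimen and have benefit probability q, while the other 26 − k have the background rate p0. Then

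P(reject) = Σ over i = 0…k of C(k, i) q^i (1 − q)^(k − i) × P[Bin(26 − k, p0) ≥ 10 − i].

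The documents give neither k nor q, so both are assumptions.

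Worked case, k = 2, q = 0.50, p0 = 0.25:
0.25 × 0.0547 + 0.50 × 0.1213 + 0.25 × 0.2338 = 0.0137 + 0.0607 + 0.0584 = 0.133.

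| k of 26 | q = 0.30 | q = 0.50 |
|---|---|---|
| 0 | 9.1% | 9.1% |
| 2 | 9.9% | 13.3% |
| 5 | 11.2% | 21.8% |

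For k = 5 and q = 0.50 the average benefit rate is (5 × 0.50 + 21 × 0.25)/26 = 29.8%.

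**3. Sensitivity to the background rate.** Section 13.2 cites about 20% progression-free at 6 months, below the 25% null. With p0 = 0.20 the type I error is 2.3%, and k = 5 at q = 0.50 gives 9.9%.

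**4. Scan timing.** The earliest permitted scan is day −28. The latest permitted chemotherapy, small-molecule or radiation dose falls just over 14 days before Day 1. The scan can therefore precede that dose by up to about 28 − 14 = 14 days, unless screening under 5.5.3 is taken to have begun by the scan. Section 3.2.8 names no interval for antibody biologics. The only other timing rule, 3.2.1, covers investigational agents (4 weeks).

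**The case against.** **A safeguard exists.** Exclusion 3.2.14 lets the treating investigator exclude a patient whose previous therapy might confound the results. That is a fair point, but it depends on individual judgment. It does not direct the investigator to ask about progression on the last regimen, so it narrows the gap without closing it.

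**The exposed group is narrow.** It needs progression after platinum, a later agent stopped without progression, residual measurable disease, and then a new line of treatment. Section 3.1.7 caps non-platinum cytotoxic regimens at one. This stands, and the documents give no frequency.

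**Benefit is not easily credited.** Stability must last 24 weeks with scans every 8 weeks. Progression is judged from the smallest sum on study, baseline included. A tumor already reduced by earlier therapy needs a further 30% decrease to be a partial response. Residual drug effect alone is therefore a weak route to success; disease already controlled at entry is the stronger one.

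**The scan gap is partly closed and runs both ways.** On the natural reading of 5.5.3, screening is under way once the baseline scan is done, and other therapy is then prohibited. An old scan in growing disease also understates baseline and pushes toward early progression. What remains is an undefined start of screening, without a clear direction of bias. A reader might infer more: that a lesion scanned, then irradiated before Day 1, would be read as a response. The documents do not support resting the point on this. Section 5.5.3 lists radiation among the prohibited treatments, with only a limited exception discussed with the overall PI, and the protocol adopts RECIST 1.1, whose full rules are not reproduced.

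**The null has slack.** If the background is 20%, the rule tolerates some carry-over. That is true, but the plan claims error control at 25%. Whether the benchmark control arm already contained such patients cannot be determined from the documents.

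**Conclusion.** The concern holds in limited form. As written, eligibility does not ensure that disease was progressing after the most recent cytotoxic or biologic regimen, and the primary endpoint can credit that regimen's control to the study drugs. The scan-timing gap is real but secondary, and its bias can go either way.

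The size is unknown. At the 25% null the illustrative false-positive probabilities run from 9.9% (two patients at 30%) to 21.8% (five at 50%), against the 10% limit. They rest wholly on the assumed number of patients and their assumed benefit rate. With a 20% background, five patients at 50% remain just within the limit.

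A reader might infer that the trial's type I error is in fact well above 10%. The documents do not show this, because they do not say how many such patients would enter. A reader might also infer that stable disease makes up some fixed share of the endpoint, such as half. Section 13.1 lists it as one component and gives no proportion.

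**What to change.** 1. Add to 3.1.6: *and progression, by investigator assessment, on or after the most recent cytotoxic or biologic/targeted regimen (single-agent hormonal therapy not counted, as in 3.1.7)*. The bracket is needed to keep the new sentence consistent with 3.1.7.
2. Add to sections 10 and 11.1.3: *the baseline scan must post-date the last dose of prior anticancer therapy*. This removes the dependence on when screening starts. No washout length is proposed.

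If enrolment is already advanced, abstract progression status on the last regimen from the records and report clinical benefit with and without patients who lacked it.

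The cost is amendment wording and two checklist lines. An occasional patient would not be enrolled, and another might need her baseline CT timed later. The sample size of 26, the 10-of-26 rule, the type I error of 0.0909 and the power of 0.916 are unchanged.
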